7.4.1 Catheter Insertion Highlights

- Soak and flush catheter in preservative free saline prior to insertion
- SOC patient prep, positioning and anesthesia for lumbar puncture
- Insert epidural needle through intervertebral spinous processes to the dural level (skin nick or pilot hole may be used to help with passage of the needle)
- Remove the needle stylet and observe for CSF drainage, advance slowly until CSF is returned
- A 5ml CSF sample to be taken from the needle
 - 3ml submitted for Cell counts with Differential and Chemistries
 - 2ml for biomarkers (cytokines) which must be stored in a -80° freezer until shipped to the core lab
- An additional level or re-positioned attempt can be made if no CSF is returned
- Do not perform excessive attempts to avoid potential complications such as CSF leakage, spinal headache or nerve root damage
- Insert guidewire and advance to low-mid thoracic spine, tracking dorsally

- Remove epidural needle and leave guidewire in place
- Using an OTW technique, advance catheter over the guidewire (with tension on the end of the guidewire to prevent further advancement)
- Upon reaching the guidewire tip, advance both the wire and catheter together until the catheter proximal inlet holes rest within the lumbar cistern (approximately L2-L3)
- When the catheter is in position remove the guidewire

If there is significant difficulty in gaining access, placing or positioning the catheter, abort the procedure and dress the wound per SOC. Those Subjects who have the procedure aborted due to an inability to gain access or obtain an acceptable position are classified as an “Attempt to Treat” subject and are followed according to the protocol through 2 day follow-up to assess the wound and potential adverse events related to the attempted access or catheter insertion. Subjects in the Attempt category are exited from the study after the protocol required 2 day follow-up visit.

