7.5.1 Neurapheresis Therapy Rates

Neurapheresis therapy will commence slowly at a nominal flow rate of 0.5mL/min. to accommodate the volume of hemorrhagic CSF pooled in the lumbar cistern. An increase of flow shall not occur until 1 hour of aggregate pump time has elapsed to optimize the system operation during the initial access of the pooled hemorrhage. At this time, a baseline CSF sample will be taken, see Section 7.5.7.

After the CSF sample has been taken, the MNeuro CFS will transition the system to auto mode. In this mode, an automated algorithm will adjust the flow rates to continuously optimize the Neurapheresis therapy based on system pressures. The MNeuro CFS will be present while the system is in auto mode for system oversight. During study therapy, the waste rate will be generally maintained within a range of 12-15 mL/hr as determined by the Investigator. However, at any time the Investigator may choose to manually adjust the system waste rate based on subject status.

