7.5.7 CSF Sampling During Neurapheresis

During catheter in-dwelling and Neurapheresis therapy, CSF samples will be obtained at regular intervals until the catheter is removed. A maximum of 11 CSF samples total per subject will be taken. Ten of those during catheter indwelling, though fewer may be taken if the catheter must be removed early.

Samples will be taken according to the schedule in Table 10 below. The initial CSF sample will be taken during catheter placement however, the first sample taken during catheter in-dwelling will be considered the Baseline CSF sample (pre-Neurapheresis sample) to which the later samples will be compared. The last CSF sample taken will be considered the Final sample or (post-Neurapheresis sample) which will be compared to the Baseline sample for applicable endpoint analyses. To account for different assay requirements, CSF sample volumes are different for the initial and seventh (40 hr) sample than those in between.

It is allowable to collect less CSF sample volume for completion of the Cell counts with Differentials based on site specific laboratory requirements. Current laboratory certificates are

required by the sponsor with laboratory processes to be made available upon request. Care should be taken to ensure laboratory samples are handled and processed consistently for accurate data reporting.

During catheter in-dwelling, the first sample (#2 on Table 10 below) should be taken after 1 hour ($\pm 30\text{min}$) of Neurapheresis therapy. The MNeuro CFS will assist in monitoring the therapy time in order to prepare for the sample. The next CSF sample should be taken at 8 hours ($\pm 2\text{hr}$) from catheter securement (8 hours of catheter in-dwelling) then each subsequent sample taken every 8 hours ($\pm 1\text{hr}$) from the previous scheduled sample (i.e. every 8 hours during catheter in-dwelling).

Table 3: Required CSF Samples

Sample #	Sample Metric	Required Assay	CSF Sample Volume
1	During Catheter Placement (needle stick)	Cell counts with Differential: RBC, WBC, neutrophils, lymphocytes, etc. Chemistries: Total protein, Glucose, Culture	3ml
		CSF Biomarkers (requires -80° storage until shipped) ^β	2ml ^β
2	1hr ($\pm 30\text{min}$) of Neurapheresis	Cell counts with Differential and Chemistries	3ml
3	8hr ($\pm 2\text{hr}$)*	Cell counts with Differential and Chemistries	3ml
4	16hr ($\pm 2\text{hr}$)*	Cell counts with Differential and Chemistries	3ml

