5	24hr ($\pm 2\text{hr}$)*	Cell counts with Differential and Chemistries	3ml
6	32hr ($\pm 2\text{hr}$)*	Cell counts with Differential and Chemistries	3ml
7	40hr ($\pm 2\text{hr}$)*	Cell counts with Differential and Chemistries	3ml
		CSF Biomarkers (requires -80° storage until shipped)	2ml
8	48hr ($\pm 2\text{hr}$)*	Cell counts with Differential and Chemistries	3ml
9	56hr ($\pm 2\text{hr}$)*	Cell counts with Differential and Chemistries	3ml
10	64hr ($\pm 2\text{hr}$)*	Cell counts with Differential and Chemistries	3ml
11	72hr ($\pm 2\text{hr}$)* ^γ	Cell counts with Differential and Chemistries	3ml

*time measured from catheter securement (beginning of indwelling time)

^βif a CSF sample for biomarkers was not obtained during catheter placement (sample #1), it can be done with sample #2

^γif the catheter is removed prior to reaching the 72hr indwelling limit, a final CSF sample should be taken just prior to catheter removal

Center personnel shall work with the MNeuro CFS to time the CSF sampling as to not interfere with SOC patient care. To ensure sample consistency and minimize subject impact, samples are to be taken using the automated sampling process within the system. The system is switched to “sample mode” then using sterile technique, a syringe is inserted into the three-way sample stopcock. Sample mode should be set at the nominal flow rate of 0.5ml/minute. The system will automatically fill the syringe. Once the appropriate amount of CSF has been retrieved, sample

mode can be stopped and the syringe removed. The MNeuro CFS will pause the system prior to the sample acquisition, and will leave the system paused for a short period post sampling e.g., approx. 15 min, to allow for the CSF fluid balance to recover.

Also reference the IFU for additional details in regard to CSF sampling. A de-identified laboratory print-out of the required CSF assay analyses must be provided to the Sponsor. The original laboratory results must be available for monitoring.

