 - CNS infection events will be reviewed by an independent medical monitor for whether or not the event meets the criteria above and will be used to calculate this endpoint (Number of subjects meeting CNS infection definition/Number of subjects in the Safety Population)

Secondary Efficacy endpoints:

- Mean reduction of RBCs and total protein by CSF sample post study therapy
 - This calculation utilizes the pre-Neurapheresis sample (first CSF sample taken either at the time of needle insertion or after catheter placement, whichever laboratory value is greater) as compared to the post-Neurapheresis sample (last CSF sample taken prior to catheter removal)

- Mean length of Neuro ICU stay
 - Mean length of Neuro ICU stay will be calculated by two different methods, one using physical location change, the second using criteria for critical care monitoring.

Exploratory endpoints:

- Proportion of subjects requiring additional CSF management during study therapy or on-going CSF management post study therapy
- Reduction in biomarkers of inflammation as seen in CSF, blood and physiologic manifestations post study therapy
 - Such as cytokines, white blood cell counts, neutrophil/lymphocyte ratio, SIRS
- Proportion of subjects with symptomatic complications from aSAH
 - Such as hydrocephalus, clinical vasospasm and delayed cerebral ischemia
- Analysis of endpoints by the following sub-groups for any groups that have at least 5 subjects that meet the criteria for the group;
 - Age: <45, ≥45-<60, 60 – 70 years
 - Gender: male, female
 - Enrollment Modified Fischer grade: 2, 3, 4
 - Baseline cisternal Hijdra score: ≤15, 16-20, 21-25, 26-30
 - Neurapheresis time: <16hrs, ≥16-32hrs, >32-48hrs, >48hrs
 - Other sub-groups not yet defined

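### The CSF endpoint takes the higher of two early samples as baseline, which contradicts Section 7.5.7 and can only push the reported RBC and protein reduction upward

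*Combined protocol and SAP*

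**What the plan says.** Section 10.2, under the secondary efficacy endpoints, defines the pre-Neurapheresis value for RBC and total protein as the "first CSF sample taken either at the time of needle insertion or after catheter placement, whichever laboratory value is greater". The post value is the last sample before catheter removal, with no selection.

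Section 7.5.7 defines the same term differently. It mentions the sample taken at catheter placement, then says that "the first sample taken during catheter in-dwelling will be considered the Baseline CSF sample (pre-Neurapheresis sample" and that later samples are compared with it. The last sample is the one "which will be compared to the Baseline sample for applicable endpoint analyses", so this is an analysis rule as well as a sampling instruction. The section identifies the sample: "During catheter in-dwelling, the first sample (#2 on Table 10 below) should be taken after 1 hour" of therapy, with a window of 30 minutes either way. (The table it means is the one now numbered Table 3.)

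Section 7.5.1 agrees with 7.5.7. It states that "An increase of flow shall not occur until 1 hour of aggregate pump time has elapsed", and then: "At this time, a baseline CSF sample will be taken, see Section 7.5.7".

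The two candidate samples are obtained differently. Section 7.4.1 has "A 5ml CSF sample to be taken from the needle" before the catheter is in place. For samples during in-dwelling, 7.5.7 says that "samples are to be taken using the automated sampling process within the system".

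**The concern.** Two separate faults are present.

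- **Contradiction.** One term has two definitions, both claimed for endpoint analysis. Two analysts following different sections can report different reductions from the same data.
- **One-sided selection.** The baseline is chosen because it is high, while the final value is not chosen at all. Part of any difference is then produced by the choice.

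The samples are also not interchangeable. Sample 1 comes through the needle with no therapy given; sample 2 comes through the system after about 1 hour of therapy. Under 10.2 the baseline route and therapy exposure would differ between subjects according to which result was higher. Because the choice is made on the laboratory value, the wording also lets the RBC and protein baselines come from different samples in the same subject.

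At stake is the credibility of the one secondary endpoint that measures, directly in CSF, the removal of RBCs and by-products that the study objective is about.

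**Working it through.** **1. Direction (no assumptions beyond both samples being available).** Let A be sample 1, B sample 2 and F the final sample. Since max(A,B) ≥ A and max(A,B) ≥ B in every subject:

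- max(A,B) − F ≥ B − F, and likewise against A;
- 1 − F/max(A,B) ≥ 1 − F/B, and likewise against A.

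Section 10.2 does not say whether the reduction is absolute or relative, but the result holds for the mean absolute reduction, the mean percent reduction and the percent decrease of means. The 10.2 result equals the 7.5.7 result only if sample 2 is at least as high as sample 1 in every subject.

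**2. The documents' own figures.** The only CSF reductions given are those from PILLAR (Section 2.1, percent decrease of means). Both reproduce:

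- protein: 1 − 144.09/537.36 = 73.2%;
- RBC: 1 − 1.17/2.78 = 57.9%.

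**3. Size, equal early means.** Inputs from Section 2.1:

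- RBC: mean 2.78e5, SD 2.43e5, so CV = 0.874;
- protein: mean 537.36, SD 500.70, so CV = 0.932.

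Assumed: lognormal values, the same mean m and CV for samples 1 and 2, and correlation ρ between them of 0.5 to 0.9. The documents give no value for ρ.

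- s = √ln(1 + CV²): 0.753 (RBC), 0.791 (protein)
- r = ln(1 + ρ·CV²)/s² (log-scale correlation)
- E[max]/m = 2Φ(s·√((1 − r)/2))
- Reduction reported when nothing changed: 1 − m/E[max]
- Reduction reported when the true fall is f: 1 − (1 − f)·m/E[max]

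Example, RBC at ρ = 0.7: r = 0.755 and E[max]/m = 2Φ(0.264) = 1.208. Zero change is reported as 1 − 1/1.208 = 17.2%. A true fall of 57.9% is reported as 1 − 0.421/1.208 = 65.2%.

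| ρ | E[max]/m, RBC | E[max]/m, protein | Zero change, RBC | Zero change, protein | True 57.9% (RBC) | True 73.2% (protein) |
|---|---|---|---|---|---|---|
| 0.5 | 1.273 | 1.284 | 21.5% | 22.1% | 66.9% | 79.1% |
| 0.7 | 1.208 | 1.216 | 17.2% | 17.8% | 65.2% | 78.0% |
| 0.8 | 1.169 | 1.175 | 14.4% | 14.9% | 64.0% | 77.2% |
| 0.9 | 1.118 | 1.123 | 10.6% | 10.9% | 62.4% | 76.1% |

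The excess is 4.5 to 9.0 points for RBC and 2.9 to 5.9 points for protein. A simulation of 400,000 subjects per setting, with ρ set on the log scale from 0.5 to 0.95, matched its closed form and gave a similar zero-change range: 9% to 23% (RBC) and 9% to 24% (protein).

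**4. Size, unequal early means.** With means m₁ and m₂ and θ = s·√(2(1 − r)):

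E[max] = m₁Φ(θ/2 + ln(m₁/m₂)/θ) + m₂Φ(θ/2 − ln(m₁/m₂)/θ).

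The table shows the reduction reported when the final mean equals the mean of the sample named, over both analytes and ρ from 0.5 to 0.9.

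| Sample 2 mean relative to sample 1 | Final mean = sample 1 mean | Final mean = sample 2 mean |
|---|---|---|
| 30% lower | 1% to 11% | 31% to 37% |
| 20% lower | 3% to 14% | 23% to 31% |
| Equal | 11% to 22% | 11% to 22% |
| 20% higher | 20% to 30% | 4% to 16% |

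With sample 2 averaging 20% lower, falls of 57.9% and 73.2% from sample 1 would be reported as 59% to 64% (RBC) and 74% to 77% (protein).

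**The case against.** The strongest defence is that sample 2 is not a pre-therapy sample. If it is lower because the first hour of pumping has already cleared blood, falling back on sample 1 recovers real removal. The excess over sample 2 is then partly genuine, and only the excess over sample 1 can be called bias without qualification. That stands as a caution on the last column of the second table. It supports naming sample 1 for everyone; it does not support picking the baseline by result, because the rule also picks sample 2 whenever sample 2 happens to be higher.

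Other points have some force:

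- **Possible agreement of the rules.** If sample 2 is usually the higher, 10.2 and 7.5.7 nearly coincide. With sample 2 averaging 20% higher, however, an excess of 4% to 16% over sample 2 remains.
- **The PILLAR baseline.** The documents do not say which sample gave the PILLAR pre-therapy means. If PILLAR also used the higher value, those percentages already contain the effect. They serve here only as example true falls.
- **Pre-specification.** The rule is mechanical and written in advance. That limits discretion but does not remove a bias built into the rule.
- **Timing.** Section 2.2 reports 16 subjects already treated under a previous protocol version, and the documents do not show which baseline rule that version used. Choosing a baseline now could itself be informed by data, which is a reason to show both results.
- **Consequence.** Sections 4.3 and 10 disclaim hypothesis-based endpoints, and no test, threshold or sample size rests on this endpoint. That limits the severity.

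**Conclusion.** The concern holds. Sections 7.5.7 and 10.2 define the same baseline differently, and the 10.2 version can only raise the reported reduction or leave it unchanged. The direction is algebra. The size rests on assumed lognormality, PILLAR spread and a correlation of 0.5 to 0.9: about 11% to 22% of apparent reduction from no change if the two early samples have equal means, and 3 to 9 points added to falls of the size seen in PILLAR. If sample 2 averages 20% to 30% below sample 1, the excess measured against sample 1 shrinks to between 1% and 14%.

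This should be fixed. The consequence is an upward-biased descriptive estimate for a secondary efficacy endpoint; the primary CT endpoint is unaffected.

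**What to change.** - In 10.2, delete the clause that selects the greater laboratory value.
- Name one sample as baseline for both RBC and protein in every subject, use identical wording in 7.5.7 and 10.2, and state the reason for the choice. Sample 2 fits the present 7.5.7 text and shares the final sample's route through the system, but follows about 1 hour of therapy and may understate removal. Sample 1 is the only one taken before therapy, but its route differs from that of the final sample.
- Report the result with the other sample as a pre-specified sensitivity analysis. Showing both fixed baselines side by side also answers the worry about choosing after 16 subjects have been treated.
- If the designated sample is missing, flag and count the subject; do not substitute the other sample silently.

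The cost is wording in 10.2, and in 7.5.7 and 7.5.1 as well if sample 1 is chosen. Both samples are already collected. The reported reduction is likely to be somewhat less favourable.

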4.4 Justification for Study and Design

The previous first-in-human study, PILLAR study, was completed to substantiate the feasibility and safety of Neurapheresis in aneurysmal SAH patients. As described in section 2.1, the study endpoints were met. The PILLAR-XT study is designed to further confirm safety and characterize efficacy of Neurapheresis therapy. Additionally, this study is expected to generate foundational data for development of the Neurapheresis treatment curve (e.g. time or volume processed needed to clear blood from the subarachnoid cisterns and lumbar spine). The study works in tandem with the current SOC treatments for SAH and does not detract from the established care pathways, or deny enrolled subjects proven therapies. The PILLAR-XT study utilizes the established skill sets of chosen Investigators who are already trained in the treatment and care of SAH patients and insertion/management of lumbar drains.

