10.2 Endpoint Analysis Definitions

Enrollment will be stopped when 30 subjects have been enrolled and treated with Neurapheresis for at least 16 hours, however, this amount of therapy time is not considered a complete treatment as absolute blood clearance would not be expected. This study is expected to generate foundational data for development of the Neurapheresis treatment curve (e.g. time or volume needed to clear blood from the subarachnoid cisterns and lumbar spine).

Primary Endpoints:

1. Mean reduction of cisternal blood via CT post study therapy
 - a. Pre, 36 hour and post-Neurapheresis CTs will be evaluated by an independent neuroradiology core laboratory for quantification of blood volume. The core lab will utilize a three (3) member team for independent review of the primary endpoint with agreement of at least two (2) reviewers required.
 - b. Mean volumes will be compared using a paired t-test with an alpha level of .05. Pre blood volume will be compared to both the 36-hour and post-Neurapheresis blood volumes separately to support creation of the therapy curve. However, the Pre to Post Neurapheresis comparison will be the primary endpoint measure.
 - c. An analysis of variance may be considered based on results from exploratory sub-groups analyses
2. Proportion of subjects with Neurapheresis Catheter, System or Therapy related serious adverse events
 - a. Events will be reviewed by an independent medical monitor for relatedness and will be used to calculate this endpoint (Number of subjects with related SAEs/Number of subjects in the Safety Population)

Secondary Safety Endpoints:

- Proportion of subjects with successful catheter placement
 - This only includes the subjects in whom catheter placement was attempted (Number of subjects with catheter attempted/Number of subjects in the Safety Population)
- Proportion of subjects with device or study therapy related adverse events
 - Events will be reviewed by an independent medical monitor for relatedness and will be used to calculate this endpoint (Number of subjects with related AEs/Number of subjects in the Safety Population)
- Proportion of subjects with systemic CNS infection within 5 day of catheter removal
 - In order to be considered a CNS infection, the following must be true; abnormal growth was identified on CSF culture within 5 days of catheter removal, subject has physiologic symptoms of infection and treatment was administered specifically for that infection.

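### Section 10.2 plans no within-subject time- or volume-course analysis of CSF red cells or protein, though serial samples and processed volume are recorded and a lumbar treatment curve is a stated aim

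*Combined protocol and SAP*

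**What the plan says.** **Aim.** Section 4.4 expects the study to produce foundational data for a treatment curve, described as the "time or volume processed needed to clear blood from the subarachnoid cisterns and lumbar spine". Section 10.2 repeats this almost word for word: "time or volume needed to clear blood from the subarachnoid cisterns and lumbar spine".

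**Data collected.** Section 7.5.7 states: "A maximum of 11 CSF samples total per subject will be taken". The first is at the needle stick, the next after 1 hour of therapy, the next at 8 hours from catheter securement, "then each subsequent sample taken every 8 hours". Table 3 lists "Cell counts with Differential and Chemistries" or the equivalent for every sample, so RBC and total protein are measured each time. Section 7.5.3 lists processed volume among the data the system records.

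**Analysis planned.** In Section 10.2 the pre value is the "first CSF sample taken either at the time of needle insertion or after catheter placement, whichever laboratory value is greater". It is used "as compared to the post-Neurapheresis sample (last CSF sample taken prior to catheter removal"). The only analysis that Section 10.2 ties to the curve is of CT blood volume: pre against 36 hours and pre against post.

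**Two related statements.** Section 7.5.7 says the first in-dwelling sample "will be considered the Baseline CSF sample (pre-Neurapheresis sample) to which the later samples will be compared", but gives no method and then names only the final sample for endpoint analyses. The exploratory list in Section 10.2 analyses endpoints by Neurapheresis-time band where a band holds at least five subjects.

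**The concern.** Head CT informs the cisternal part of the curve. The lumbar part can come only from the CSF samples, and a first-to-last difference gives one net change per subject. It does not show how concentration falls as pump time or processed volume accumulates.

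The mean of those differences also mixes exposures. Under Section 5.7.1 a subject counts as treated once therapy has started and is then used in all analyses. Section 7.5 sets a pump-time limit for the first five subjects under this protocol that may be lifted for later ones, within a 72-hour dwell.

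At stake is whether the lumbar curve rests on a method fixed in advance or on one chosen after the data are seen.

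**Working it through.** **1. Sample count (Table 3).** Needle stick 1 + one at 1 hour of therapy + nine at 8, 16, …, 72 hours = 11, of which 10 are in-dwelling. This reproduces the plan's figures.

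**2. Samples used.** The pre value draws on samples 1 and 2 and the post value is the last, so at most three contribute. For a subject who reaches 72 hours, 11 − 3 = 8 (samples 3 to 10) enter no specified RBC or protein analysis.

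**3. Earlier-study figures (Section 2.1, N=13).** RBC: 1 − 1.17/2.78 = 57.9%. Protein: 1 − 144.09/537.36 = 73.2%. Both match the plan.

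**4. Spread of exposure (Section 2.1).** Pump time ran from 5:32 to 24:00 hours, 24/5.53 = 4.3-fold. Processed volume ran from 180.6 to 1447.6 mL, 1447.6/180.6 = 8.0-fold. The limits then were 24 hours of pump time and 36 hours of dwell; the present protocol allows more.

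**5. What the intermediate samples could add in precision.** Let σ be the within-subject residual SD and τ the between-subject SD of the change. The documents give neither, so their ratio is varied. All samples are placed on one clock, at 1, 8, 16, … hours, with L the span from first to last.

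- Variance of one subject's change from two points: τ² + 2σ²
- From a straight line through all in-dwelling samples: τ² + (L²/Sxx)σ², where Sxx = Σ(t − t̄)²

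For ten samples, t̄ = 36.1, Sxx = 18,241 − 10 × 36.1² = 5208.9, L = 71 and L²/Sxx = 5041/5208.9 = 0.968. With τ = 0 the variance ratio is 2/0.968 = 2.07. The SE ratio (line over two points) is √[(τ² + (L²/Sxx)σ²)/(τ² + 2σ²)]:

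| Last sample | Samples | L²/Sxx | τ²=0 | τ²=σ² | τ²=4σ² |
|---|---|---|---|---|---|
| 16 h | 3 | 1.997 | 1.00 | 1.00 | 1.00 |
| 24 h | 4 | 1.783 | 0.94 | 0.96 | 0.98 |
| 40 h | 6 | 1.407 | 0.84 | 0.90 | 0.95 |
| 72 h | 10 | 0.968 | 0.70 | 0.81 | 0.91 |

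These assume independent residuals. For ten samples to 72 hours with generalised least squares, and τ² from 0 to 4σ², an 8-hour autocorrelation of 0.5 gives ratios of 0.93 to 0.98. An autocorrelation of 0.7 gives 0.985 to 0.995. The reduction in SE therefore runs from about 0% to 30%.

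**6. Sensitivity to curve shape.** Suppose log concentration falls to a plateau with an 8-hour half-life. As a fraction of the full fall, the true change from 1 to 72 hours is 0.915, while a straight line estimates 0.714, about 22% too small (1 − 0.714/0.915). With a 48-hour half-life the figures are 0.632 and 0.626. Curvature must therefore be allowed.

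**7. Precision of the headline endpoint.** Take the earlier-study SDs and 30 subjects. The SD of the RBC difference is √(2.43² + 1.30² − 2ρ × 2.43 × 1.30) × 10⁵. The change of 1.61 × 10⁵ cells/µL then has a 95% CI half-width of 1.03 × 10⁵ at ρ = 0, 0.79 × 10⁵ at 0.5 and 0.52 × 10⁵ at 0.9. The correlation ρ is an assumption.

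**The case against.** The strongest reply is that this is a feasibility study with no hypothesis-based endpoint. It promises data for developing a curve, and the curve itself is neither an objective (Section 4.1) nor an endpoint (Section 4.3). The samples and the volume log are such data and could be modelled later. That stands: a reader might infer that the trial cannot state the lumbar time or volume to clearance, and the documents do not support this. What is missing is a pre-specified method.

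A reader might also infer that the lumbar data have no analysis beyond a first and a last value. That goes too far. Up to three samples feed the endpoint, Section 7.5.7 mentions comparing later samples with baseline, and the time bands would split the RBC and protein endpoint by exposure. None of these fills the gap. The bands compare different subjects, whose duration depends partly on clinical course, and use neither the intermediate samples nor volume. Their cut-points also differ between Section 4.3 (28 and 40 hours) and Section 10.2 (32 and 48 hours).

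The third tempting inference is that precision is being given away by a factor of two in variance. The 2.07 needs all ten samples, a straight line, independent errors and no variation in slope between subjects. It also concerns a fitted slope, whereas the endpoint is a mean change from a greater-of-two baseline. With complete data, a model with unstructured time returns the same first-to-last contrast, so any gain comes from assuming a shape. The plan sets no precision target that could be missed.

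Two cautions about the remedy also stand. Processed volume is determined after baseline: the algorithm sets flow from system pressures (Section 7.5.1) and therapy pauses with clinical status (Section 7.5). And 16 subjects were treated under a previous protocol version (Section 2.2) whose sampling schedule is not in these documents.

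**Conclusion.** The point holds as a gap in pre-specification. Section 10.2 contains no within-subject time- or volume-course analysis of CSF RBC or protein. Up to eight of eleven samples per subject and all the processed-volume data are left out of the specified RBC and protein analyses, while the lumbar part of the curve is a stated aim. This rests on the text and needs no assumption.

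The first-to-last mean is a usable headline, but it pools exposures that differed about four-fold in pump time and eight-fold in volume in the earlier study. The precision argument is secondary: 0% to 30% off the SE, with the upper end reached only under favourable assumptions. This is a worthwhile, low-cost addition and not a defect that invalidates the endpoint.

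**What to change.** Keep the first-to-last reduction as the headline and add a supplementary analysis to Section 10.2:

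- Model log RBC and log total protein on all available in-dwelling samples, with subject random effects and residual serial correlation.
- Index on cumulative pump time and, in a separate model, on cumulative processed volume at each sample. This also avoids mixing clocks, since sample 2 is timed by therapy and later samples by catheter securement.
- Allow curvature with a spline or a plateau term, and plot individual profiles.
- Report time and volume to 50% reduction, and to 90% if reached, with 95% CIs and only within the observed range. The earlier study's fall in mean RBC was 57.9%, so 90% may lie outside it.
- Describe the results as single-arm and descriptive: natural clearance and any drainage through the EVD contribute, and volume is set after baseline. State the assumption made about series cut short by early catheter removal.
- Reconcile the two baselines. Section 7.5.7 takes the first in-dwelling sample and Section 10.2 the greater of two. If the two values were exchangeable and normal, taking the greater would raise the pre value by 1/√π = 0.56 within-subject SD.
- Reconcile the time bands in Sections 4.3 and 10.2.

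No new samples are needed. The cost is SAP text, analysis work and some dependence on the model. The series may be sparser for the 16 earlier subjects, which leaves 30 − 16 = 14 on the present schedule; check the earlier schedule before fixing the model's complexity.
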